6.5.1 Dose Modifications for RXC004

RXC004 dose reduction and interruption are permitted.

RXC004 may be dose interrupted (withheld) until a clinically significant (any grade) and/or a grade ≥ 3 related adverse event resolves to baseline or \leq grade 2. RXC004 may also be withheld if it is necessary to give a concomitant medication that is a moderate or strong CYP3A4 inhibitor.

Colitis events may occur with RXC004 or with pembrolizumab, and should be managed per Appendix K and, for participants in Module 3, the dose modification and toxicity management guidelines for irAEs associated with pembrolizumab (Appendix L 1) if applicable. For patients receiving the combination treatment with RXC004 and pembrolizumab, the most conservative guideline should be followed.

RXC004 dose interruption and stopping criteria are detailed in Table 11.

Table 11 RXC004 Dose Modification and Stopping Criteria

Event	Action
Colitis events (e.g. Colitis, ileitis, enterocolitis etc)	
Grade 1	Reduce RXC004 to a lower dose (see Table 12 for dose reduction scheme) and manage per Appendix K. If receiving RXC004 in combination with pembrolizumab, no additional action is required for pembrolizumab.
Grade 2	Interrupt RXC004. Manage as per Appendix K. When event has resolved to Grade $\leq 1^a$ and steroids have been tapered to prednisolone ≤ 10 mg per day (or equivalent), resume RXC004 at a lower dose (see Table 12 for dose-reduction scheme). If event recurs after re-starting study treatment, then RXC004 should be permanently discontinued. If receiving RXC004 in combination with pembrolizumab, interrupt pembrolizumab and see Appendix L for guidance.
Grade 3	Interrupt RXC004. Manage as per Appendix K. When event has resolved to Grade $\leq 1^a$ and steroids have been tapered to ≤ 10 mg of prednisolone per day (or equivalent), resume RXC004 at a lower dose (see Table 12 for dose reduction scheme). If event recurs after re-starting study treatment, then RXC004 should be permanently discontinued. If receiving RXC004 in combination with pembrolizumab; permanently discontinue both agents and manage as per Appendix K and Appendix L.
Grade 4	If receiving RXC004, either as monotherapy or in combination with pembrolizumab: Permanently discontinue both agents. Manage per Appendix K and Appendix L.
Dysgeusia events	

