7 DISCONTINUATION OF STUDY TREATMENT AND PARTICIPANT DISCONTINUATION/WITHDRAWAL

7.1 Discontinuation of Study Treatment

An individual patient will not receive any further IP if any of the following occur:

- Patient decision to withdraw from further treatment with IP. The patient is, at any time, free to discontinue treatment, without prejudice to further treatment.
- Clinical or RECIST 1.1-defined radiological progression. (Symptomatically/clinically

stable patients may continue treatment until symptomatic/clinical progression or second RECIST 1.1 progression [relative to the first ‘on study treatment’ RECIST 1.1 progression]. See Section 7.1.1 for details for continuing study treatment after RECIST1.1 defined progression.

- An AE that meets RXC004 discontinuation criteria in Table 11.
- Pregnancy or intent to become pregnant.
- Initiation of alternative anticancer therapy including another investigational agent .
- Non-compliance with the study protocol that, in the opinion of the Investigator or Sponsor, warrants withdrawal from treatment with IP.

For participants in Module 3 (RXC004 in combination with pembrolizumab), the following additional criteria for discontinuation of pembrolizumab apply:

- Completion of 18 administrations (approximately 2 years) with pembrolizumab (q6w dosing). [Note: The number of administrations is calculated starting with the first dose of pembrolizumab.]
- Any study intervention-related toxicity specified as a reason for permanent discontinuation of pembrolizumab as defined in the guidelines for dose modification due to AEs in Appendix L.
- Discontinuation of treatment may also be considered for participants who have attained a confirmed complete response (CR) and have been treated for at least 24 weeks, receiving at least 2 doses of pembrolizumab beyond the date when the initial CR was declared.

Discontinuation from study treatment is NOT the same thing as a withdrawal from the study. If study treatment is permanently discontinued, the participant will remain in the study to be evaluated for safety, progression (if the patient discontinues for a reason other than progression) and survival. See the Schedule of Assessments (Table 15, Table 16, and Table 18) for data to be collected at the time of discontinuation of study treatment and during follow-up.

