Appendix K Management of Colitis Events

In the Phase 1 study of RXC004, events of colitis or enteritis were reported in four patients who commenced treatment at doses of 3 mg QD or 10 mg QD. At the time of publishing this protocol, an SAE of Grade 3 enteritis has been reported in 1 patient out of 12 patients dosed in the Phase 2 study RXC004/0002 and an SAE of Grade 3 colitis has been reported in 1 patient out of 21 patients dosed in this Phase 2 study (RXC004/0003). Both patients were receiving RXC004 2 mg QD. The enteritis and the colitis events were both considered by the Investigator as RXC004-related.

RXC004-related diarrhoea/colitis may present as abdominal pain with other symptoms including intermittent constipation, diarrhoea, nausea and/or vomiting. In some cases, symptoms may be minimal. Blood and mucus in the stool may not be apparent. Symptoms may be preceded by or accompanied by a raised CRP and neutrophil count.

Pembrolizumab is also known to cause irAEs including colitis.

If lower GI-tract inflammation is suspected, infectious and other causes should be excluded, including CMV and *C. difficile*. Attempts should be made to definitively diagnose the condition with a CT scan and colonoscopy/sigmoidoscopy with biopsy, if clinically safe to do so.

Management:

Monitoring of CRP or fecal calprotectin levels may help to monitor the response to treatment.

Table 19 Management of Colitis Events

Event and grade	Management
Grade 1 colitis (asymptomatic but evidence on CT scan)	Continue RXC004 at a lower dose and repeat the CT scan within 4 weeks. No action is needed for pembrolizumab. No additional treatment is indicated. If the Grade 1 colitis is evident on- the second scan despite the lower dose of RXC004, it should be managed as Grade 2 colitis and the scan should be repeated within 4 weeks.
Grade 2 colitis (abdominal pain, mucus or blood in stool)	Pause RXC004 and pembrolizumab (if applicable).

Event and grade	Management

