	
Manage with corticosteroids at a dose of 1-2 mg/kg methylprednisolone equivalent.
 
When symptoms have resolved, taper over 2-4 weeks.
 
If symptoms recur during tapering, the steroid dose may need to be increased again.
 
If no improvement in 72 hrs despite treatment, treat as Grade 3.
 
RXC004 can be restarted at a lower dose after colitis has resolved to Grade $\leq 1^*$ and steroids tapered to physiological levels (<10 mg prednisolone per day equivalent dose) over at least 1 month.
 
If steroids cannot be tapered to physiological levels within 12 weeks of commencing steroid treatment, then RXC004 and pembrolizumab (if applicable) should be permanently discontinued.

Grade 3 colitis (severe or persistent abdominal pain, fever, ileus; peritoneal signs)	
Pause RXC004 and pembrolizumab, if applicable.
 
Seek specialist advice.
 
Manage with corticosteroids at a dose of 1-2 mg/kg methlyprednisolone equivalent.
 
When symptoms improve, taper steroids to physiological levels over 4-8 weeks and consider use of prophylactic antibiotics and anti-fungals.
 
RXC004 can be restarted at a lower dose after colitis has resolved to Grade $\leq 1^*$ and steroids tapered to physiological levels

Event and grade	Management
	
(<10 mg prednisolone per day equivalent dose)
 
If steroids cannot be tapered to physiological levels within 12 weeks of commencing steroid treatment, then RXC004 and pembrolizumab, if applicable, should be permanently discontinued
 
Additional anti-inflammatory medications (e.g. infliximab) may be indicated if no improvement in 48-72 hrs. It is important to rule out bowel perforation and refer to infliximab SMPC/USPI for general guidance before using infliximab.
 
If anti-inflammatories are required RXC004 and pembrolizumab, if applicable, should be permanently discontinued.

Grade 4 colitis (life-threatening consequences)	
Manage as Grade 3 colitis.
 
RXC004 and pembrolizumab, if applicable, should be permanently discontinued.

*Attempts should be made to confirm that the colitis has resolved to Grade ≤ 1 (e.g. normalised CRP or fecal calprotectin if raised during event; GI appearance normalised on X ray/ CT or endoscopy) before restarting RXC004.

If there is any recurrence of colitis \geq Grade 2 after recommencing RXC004, **RXC004 and pembrolizumab, if applicable, should be permanently discontinued.**

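### Table 11 states no grade for the colitis recurrence that permanently stops RXC004, Appendix K sets it at Grade 2 or higher, and nothing settles a Grade 1 finding after restart on monotherapy

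*Protocol*

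**What the plan says.** Colitis on RXC004 is governed by two parts of the protocol.

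- **Table 11 (Section 6.5.1), Grade 2 and Grade 3 rows.** RXC004 is interrupted, then resumed at a lower dose once the event is at Grade 1 or below and steroids are tapered. Both rows continue: "If event recurs after re-starting study treatment, then RXC004 should be permanently discontinued".
- **Table 11, Grade 1 row.** "Reduce RXC004 to a lower dose (see Table 12 for dose reduction scheme) and manage per Appendix K".
- **Appendix K, sentence after Table 19.** "If there is any recurrence of colitis" of Grade 2 or higher after RXC004 is recommenced, RXC004 is permanently discontinued, and pembrolizumab too where it applies.
- **Appendix K, Table 19, Grade 1 row.** "Continue RXC004 at a lower dose and repeat the CT scan within 4 weeks". If Grade 1 colitis is still evident on that second scan, it is handled as Grade 2.

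Three further sentences determine which of these a site would apply. Section 7.1 lists as a reason to stop treatment: "An AE that meets RXC004 discontinuation criteria in Table 11". Section 6.5.1 says: "Colitis events may occur with RXC004 or with pembrolizumab, and should be managed per Appendix K". It then adds: "For patients receiving the combination treatment with RXC004 and pembrolizumab, the most conservative guideline should be followed".

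**The concern.** Both passages are in force, and they define the trigger for an irreversible action differently: one with no grade, one with a threshold. They part at a Grade 1 finding after restart. Appendix K describes Grade 1 colitis as asymptomatic with evidence on CT. Patients have CT or MRI every 6 weeks for the first 54 weeks, so such a finding could come to light without symptoms.

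The first thing at stake is the patient's treatment. The second is consistency of the safety data. Discontinuations are a safety endpoint (Protocol Section 3), and colitis is an adverse event of potential interest (Section 8.3.13). The SAP tabulates treatment-emergent events leading to permanent discontinuation of RXC004 (Section 4.12.1) and summarises duration, cumulative dose and RDI (Section 4.10). In small single-arm cohorts, those summaries should not depend on which page a site consulted.

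**Working it through.** The plan gives no figure to reproduce here, so the check sets the passages side by side. Take a monotherapy patient (Module 1 or 2) who restarted RXC004 after Grade 2 or Grade 3 colitis.

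| Finding after restart | Table 11 | Appendix K | Same action? |
|---|---|---|---|
| Grade 2 or higher | Permanent stop | Permanent stop | Yes |
| New Grade 1 | Stop, if the recurrence sentence is read literally; dose reduction, if the Grade 1 row is applied | No stop required; the Grade 1 row continues at a lower dose with a repeat scan | Not settled |
| Grade 1 still evident on the second scan | As above | Managed as Grade 2, without saying whether this is a recurrence of Grade 2 or higher | Not settled |
| Residual Grade 1 already present at restart | Counts as resolved for restart; not stated whether its persistence is recurrence | Same | Not settled |

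**Which text prevails on monotherapy?** Section 7.1 favours Table 11. Section 6.5.1 and the colitis rows of Table 11 themselves refer on to Appendix K. The tie-break is worded for the combination only.

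**Combination patients.** For Module 3, Table 11 stops both agents at the first Grade 3 event, so restart arises there only after Grade 2, and the tie-break applies. The gap therefore concerns mainly Modules 1 and 2.

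**Lowest dose cohort.** In Module 2 Cohort 2 the first reduction is to 0.5 mg, and Table 12 lists no lower level. The Grade 1 action of a further reduction then has no listed dose, so the practical difference between the passages is narrower there.

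**How often.** Sections 2.3.1.2 and Appendix K report Grade 3 colitis in 1 of 21 patients dosed in this study (1/21 = 4.8%) and Grade 3 enteritis in 1 of 12 in the sister study (1/12 = 8.3%), both at 2 mg daily. The disputed case also needs a restart and then a Grade 1 finding. The documents report no such patient, and those passages give no count of Grade 2 events at 2 mg in the Phase 2 studies.

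**Effect on the summaries.** SAP Section 4.10 divides cumulative dose by days on treatment times 2 mg for Modules 1 and 2. Suppose a patient who started at 2 mg and restarted at 1.5 mg is reduced again to 1 mg. Each further day taken at that dose adds 1 mg to the numerator and 2 mg to the denominator (1/2 = 50%), which pulls RDI toward 50% while treatment lengthens. A permanent stop instead fixes duration at the last dose and adds one discontinuation.

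**PFS.** Protocol Section 9.4.2.2 and SAP Section 3.2.1.1 follow PFS whether or not the patient leaves study treatment.

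**The case against.** The best defence is that the passages can be read in harmony. The recurrence sentence sits in rows headed Grade 2 and Grade 3, directly after those rows treat Grade 1 or below as resolved. On that reading, an event recurs when it rises above Grade 1 again, which is Appendix K's threshold. The same rows refer to Appendix K, which could be supplying the detail, and Table 11's own Grade 1 row reduces the dose just as Appendix K does.

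Much of this stands. A reader might infer that Table 11 orders a stop for recurrence at any grade. It does not say so; it states no grade, and part of the ambiguity lies inside Table 11 itself. Nor does Appendix K's Grade 1 row mention recurrence after restart: continuation is inferred from the Grade 2 threshold.

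The harmonising reading is not written down, however. Where the protocol limits other repeat events by grade it prints the grade, as in the Grade 3 repeat-toxicity entries of Tables 11 and 12. A literal reading of the colitis rows is therefore reasonable, and it stops a patient whom Appendix K does not require to stop.

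It can also be argued that Section 7.1 already gives Table 11 precedence. That identifies the table but not what recurrence means in it, and Section 6.5.1 points colitis to Appendix K as well.

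**Conclusion.** The inconsistency is real but narrow. The two passages agree on recurrence at Grade 2 or higher. They do not settle a Grade 1 finding after restart, and no tie-break covers monotherapy. Few patients are likely to be affected; the cohort sizes are redacted, so no count can be given. For any such patient the difference is between a permanent stop and continued dosing. In the analysis it can move discontinuation counts, exposure and RDI by a few patients.

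Three stronger inferences are not supported:

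- **That Grade 1 findings after restart are to be expected.** Both passages ask for attempts to confirm resolution before restart. Such findings are possible; their frequency is unknown.
- **That Phase 1 measures the problem.** Two patients there had recurrence after initially responding to steroids. The protocol gives neither the grade of those recurrences nor whether RXC004 had been restarted, and all four patients with intestinal inflammation began at 3 mg or more.
- **That the primary endpoint of Modules 1 and 2 is compromised.** Stopping is not itself a PFS event or a censoring reason. The only link is through time on drug.

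The conclusion assumes that sites may consult either passage, since the protocol directs them to both.

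**What to change.** Reconcile the Grade 1, 2 and 3 colitis rows of Table 11 with the Grade 1 row and closing sentence of Appendix K:

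1. State in both places the same recurrence grade that triggers permanent discontinuation of RXC004.
2. Say whether Grade 1 colitis already present at restart counts as recurrence.
3. Say whether Grade 1 colitis managed as Grade 2 after a second scan counts as recurrence.

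The sponsor decides which rule stands; this review takes no position on it. The cost is about one sentence in each place and no change to the design or analysis. There is a precedent: the amendment history for Version 4.0 records removal of a Section 6.5 limit on interruptions for situations where it conflicted with Appendix K's colitis advice.

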4.4.1.2 RXC004 Safety Data in Combination with Nivolumab

As of 01 July 2022, 13 patients have received RXC004 in combination with nivolumab 480 mg Q4W at doses of RXC004 1 mg and 1.5 mg QD in Module 2 of the ongoing Phase 1 study RXC004/0001. Eight of these patients received treatment at the highest declared tolerated dose (RXC004 1.5 mg). Treatment related AEs of CTCAE \geq Grade 2 reported in DLT-evaluable patients are summarised in Table 5.

Overall, the AE profile of the RXC004 1.5 mg dose in combination with nivolumab is similar to the RXC004 2 mg monotherapy dose. More patients who received the 1.5 mg dose had treatment related AEs of Grade 2 or higher (4/6) than patients who received the 1 mg dose (2/5). One patient who received 1.5 mg in combination had drug-induced liver injury (DILI), which was considered drug-related and a DLT.

The SRC determined at a meeting held on 07 July 2022, that both RXC004 1 mg and 1.5 mg QD in combination with nivolumab are tolerated doses. A decision was made not to further escalate the dose in the study, based on the safety and PK profiles of the 1.5 mg dose, as the combination of RXC004 2 mg with nivolumab was anticipated to lead to slightly higher exposure and potentially more AEs than the 2 mg monotherapy dose.

Table 5 Treatment-related AEs Grade 2 or higher including DLTs, observed in DLT evaluable patients as of 01 July 2022, Phase 1 study RXC004/0001 Module 2 (RXC004 + nivolumab)

Dose	Number of patients dosed	Patients evaluable for DLT	Study treatment-related AEs, CTCAE \geq Grade 2 in DLT-evaluable ^a patients
1.0 mg QD RXC004 + nivolumab 480 mg q4w	5	5	
Tolerated dose
 
Events \geq Grade 2 in DLT-evaluable patients (2/5 patients):
 
G2 back pain (1/5 patients) ^b G2 nausea (1/5 patients) ^b G2 fatigue (1/5 patients) ^c G2 poor appetite (1/5 patients) ^c G3 fatigue (1/5 patients) ^b

1.5 mg QD RXC004 + nivolumab 480 mg q4w	8	6 ^e	
Tolerated dose
 
Events \geq Grade 2 in DLT evaluable patients (4/6 patients):
 
G2 dysgeusia (2/6 patients) ^b G2 diarrhoea (1/6 patients) ^b G2 diarrhoea (1/6 patients) ^c G2 reduced appetite (1/6 patients) ^b G2 nausea (1/6 patients) ^b G2 constipation (1/6 patients) ^d G2 anorexia (1/6 patients) ^b G2 increased total bilirubin (1/6 patients) ^b G2 high total bilirubin (1/6 patients) ^b G3 drug-induced liver injury (1/6 patients) [DLT] ^c

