^a The DLT assessment period ran from the start of dosing with RXC004 (Cycle 0 Day 1) up to Cycle 1 Day 28. To be evaluable for DLT assessment patient must have received \geq 66% of the intended dose of RXC004 and all of the nivolumab infusion during Cycle 1, or experienced a DLT event in the assessment period.

^b Related to RXC004.

^c Related to RXC004 and nivolumab.

^d Related to nivolumab.

^e Two of the 8 patients who received RXC004 1.5 mg in combination with nivolumab discontinued prior to the end of Cycle 1 without meeting DLT criteria, and were replaced.

AE, adverse event; CTCAE, Common Terminology Criteria for Adverse Events; DLT, dose-limiting toxicity; q4w, every 4 weeks; QD, once daily.

Table 6 summarises the TEAEs reported with RXC004 + nivolumab by category.

**Table 6 Summary of TEAEs, as of 01 July 2022, Phase 1 study RXC004/0001
Module 2 (RXC004 + nivolumab)**

Category of TEAE	Number (%) of patients		
	RXC004 1.0 mg + nivolumab (N = 5)	RXC004 1.5 mg + nivolumab (N = 8)	Overall (N = 13)
TEAE	5 (100)	8 (100)	13 (100)
Treatment-related TEAE	5 (100)	8 (100)	13 (100)
TEAE \geq Grade 3	3 (60)	4 (50)	7 (54)
Treatment-related TEAE \geq Grade 3	1 (20)	3 (38)	4 (31)
TEAE \geq Grade 4	0 (0)	0 (0)	0 (0)
Serious TEAE	3 (60)	3 (38)	6 (46)
Serious treatment-related TEAE	0 (0)	1 (13)	1 (8)
TEAE leading to discontinuation of study treatment (RXC004)	0 (0)	2 (25)	2 (15)
Treatment-related TEAE leading to discontinuation of study treatment	0 (0)	2 (25)	2 (15)
TEAE leading to RXC004 dose modification	2 (40)	5 (63)	7 (54)
Dose reduced	0 (0)	1 (13)	1 (8)
Dose interrupted	2 (40)	5 (63)	7 (54)
TEAE leading to death	0 (0)	0 (0)	0 (0)
TEAE of dose-limiting toxicity	0 (0)	1 (13)	1 (8)

AEs were coded using MedDRA Version 24.1. A TEAE was an AE with onset on or after date of first dose of study treatment and within 30 days of last dose.

Treatment-related AE was an AE that had relationship to study drug designated by the investigator as Possibly Related or Probably Related.

Treatment-Related: AEs related to RXC004 and/or nivolumab. If the relationship to RXC004 or nivolumab was missing, the event was conservatively treated as related to the corresponding study treatment.

AE, adverse event; MedDRA, Medical Dictionary for Regulatory Activities; TEAE, treatment-emergent adverse event.

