The most common TEAEs (that were reported by more than one patient) are summarised by RXC004 dose level and overall in Table 7. The most common TEAEs were decreased appetite, fatigue, and nausea which were all reported for 6 patients each (46%).

Table 7 Most common TEAEs, as of 01 July 2022, Phase 1 study RXC004/0001 Module 2 (RXC004 + nivolumab)

Preferred term	Number (%) of patients		
	RXC004 1.0 mg QD + nivolumab (N = 5)	RXC004 1.5 mg QD + nivolumab (N = 8)	Overall (N = 13)
Patients with any TEAEs	5 (100)	8 (100)	13 (100)
Decreased appetite	2 (40)	4 (50)	6 (46)
Fatigue	3 (60)	3 (38)	6 (46)
Nausea	2 (40)	4 (50)	6 (46)
Dysgeusia	1 (20)	4 (50)	5 (38)
Constipation	2 (40)	2 (25)	4 (31)
Headache	2 (40)	2 (25)	4 (31)
Weight decreased	1 (20)	3 (38)	4 (31)
Abdominal distension	1 (20)	2 (25)	3 (23)
Blood bilirubin increased	0 (0)	3 (38)	3 (23)
Pruritus	1 (20)	2 (25)	3 (23)
Urinary tract infection	0 (0)	3 (38)	3 (23)
Abdominal pain	0 (0)	2 (25)	2 (15)
Alanine aminotransferase increased	0 (0)	2 (25)	2 (15)
Aspartate aminotransferase increased	1 (20)	1 (13)	2 (15)
Back pain	1 (20)	1 (13)	2 (15)
Blood alkaline phosphatase increased	0 (0)	2 (25)	2 (15)
Diarrhoea	0 (0)	2 (25)	2 (15)
Hyperthyroidism	1 (20)	1 (13)	2 (15)
Vomiting	0 (0)	2 (25)	2 (15)

QD, once daily; TEAE, treatment-emergent adverse event.

The most common AEs (reported by more than one patient) related to study treatment (RXC004 or nivolumab) are summarised in Table 8. All 13 patients had at least one AE related to study treatment; the most common treatment-related AEs were nausea (46%), dysgeusia (38%), and fatigue (38%). With the exception of fatigue, all of these events were more frequently observed at the 1.5 mg dose than the 1 mg dose level. Dysgeusia is considered to be an on-target effect of Wnt inhibition.

Table 8 Most common AEs considered related to RXC004 or nivolumab, as of 01 July 2022, Phase 1 study RXC004/0001 Module 2 (RXC004 + nivolumab)

Preferred term	Number (%) of patients		
	RXC004 1.0 mg QD + nivolumab (N = 5)	RXC004 1.5 mg QD + nivolumab (N = 8)	Overall (N = 13)
Patients with any TRAEs	5 (100)	8 (100)	13 (100)
Nausea	2 (40)	4 (50)	6 (46)
Dysgeusia	1 (20)	4 (50)	5 (38)
Fatigue	2 (40)	3 (38)	5 (38)
Decreased appetite	1 (20)	3 (38)	4 (31)
Weight decreased	1 (20)	3 (38)	4 (31)
Blood bilirubin increased	0 (0)	3 (38)	3 (23)
Alanine aminotransferase increased	0 (0)	2 (25)	2 (15)
Aspartate aminotransferase increased	1 (20)	1 (13)	2 (15)
Constipation	1 (20)	1 (13)	2 (15)

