Grade 1/2	RXC004 related: Manage per Appendix J Consider dose reduction, depending on clinical symptoms Interrupt RXC004 treatment if dysgeusia is associated with >5 kg weight loss from baseline.

Table 11 RXC004 Dose Modification and Stopping Criteria

Event	Action
Grade 2 associated with a 10-20% decrease in body weight	RXC004 related: Manage per Appendix J Reduce RXC004 to a lower dose (see Table 12 for dose-reduction scheme).
Grade 2 associated with a > 20% decrease in body weight	RXC004 related: Permanently discontinue RXC004. If receiving RXC004 in combination with pembrolizumab, the pembrolizumab can continue if clinical benefit is judged by the Investigator.
Other AEs	
RXC004-related Grade 3 toxicity (1st event)	Interrupt RXC004 and provide supportive care, resume a lower dose level when resolved (\leq Grade 2 or returns to baseline). See Table 12 for dose-reduction scheme.
RXC004-related Grade 3 toxicity (subsequent repeat of a previously experienced event)	Permanently discontinue the related study treatment
Any Grade 4 toxicity	Permanently discontinue the study treatment.
All Grade events	Study treatment can be interrupted or discontinued for any clinically significant AEs that in the investigator's opinion warrants treatment interruption or discontinuation.
Bone events	
Confirmed (by imaging) RXC004-related fragility bone fracture (excluding grade 1 vertebral deformities)	Permanently discontinue RXC004. Pembrolizumab can continue if the patient is receiving clinical benefit as judged by the investigator.
Patients with a DEXA scan showing >7% worsening in BMD at lumbar spine or total hip compared to baseline	Permanently discontinue RXC004. Pembrolizumab can continue if the patient is receiving clinical benefit as judged by the investigator.
An individual increase in β -CTX of CCI from the baseline (screening) value or an individual measurement of CCI	Permanently discontinue RXC004 unless the patient has received clinical benefit (investigator assessment) and continued treatment is warranted. Pembrolizumab treatment can continue if the patient is receiving clinical benefit as judged by the investigator.
COVID-19 infection	
Positive COVID-19 test	Interrupt RXC004, until acute symptoms have resolved.

Table 11 RXC004 Dose Modification and Stopping Criteria

Event	Action
Major surgery	Interrupt RXC004, resume at full dose. Pembrolizumab does not need to be interrupted. No stoppage is required for biopsy procedures.

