Vomiting	If vomiting occurs shortly after RXC004 is swallowed, the dose may be replaced if all of the intact capsules can be counted. Resume with the following scheduled dose.
Missed RXC004 dose	Allowed to take the scheduled dose up to 4 hours after the scheduled dose time. If greater than 4 hours, the missed dose should not be taken and patient should continue with next dose at allotted time.

^a Attempts should be made to confirm that the colitis has resolved to Grade ≤ 1 (e.g. normalised CRP or fecal calprotectin if raised during event; GI appearance normalised on X-ray/CT or endoscopy) before restarting RXC004.

AE, adverse event; BMD, bone mineral density; COVID-19, Coronavirus disease 2019; QD, once daily.

Toxicity will be assessed using the NCI Common Terminology Criteria for Adverse Event (CTCAE) version 5.0, unless otherwise specified. Every effort should be made to administer trial treatment at the planned dose and schedule. However, patients experiencing RXC004-related toxicities may have their RXC004 dose modified as outlined below.

RXC004 related toxicities observed during the course of the study will be managed by interruption of RXC004 and initiation of appropriate treatment as judged by the Investigator. Upon re-starting treatment the guidance for dose reduction in RXC004 contained in Table 12 should be followed.

Table 12 Guidance for Dose Reductions for RXC004-related Adverse Events

Dose Level	RXC004 (Module 1 and Module 2, Cohort 1 only)	RXC004 (Module 3 only)	RXC004 (Module 2, Cohort 2 only)
Initial dose level	2 mg QD	1.5 mg QD	1 mg QD
1st dose reduction			
• Grade 3 toxicity (1 st event)	Hold RXC004 ^b . Upon resolution to ≤ Grade 2, restart at 1.5 mg QD	Hold RXC004 ^b . Upon resolution to ≤ Grade 2, restart at 1 mg QD	Hold RXC004 ^b . Upon resolution to ≤ Grade 2, restart at 0.5 mg QD
• Grade 1/2 dysgeusia ^a	Dose reduce to 1.5 mg QD	Dose reduce to 1 mg QD	Dose reduce to 0.5 mg QD
2nd dose reduction			
• Grade 3 toxicity (1 st unique event)	Hold RXC004 ^b . Upon resolution to ≤ grade 2, restart at 1 mg QD	Hold RXC004 ^b . Upon resolution to ≤ Grade 2, restart at 0.5 mg QD	Not permitted. Permanently discontinue RXC004.
• Grade 3 toxicity (recurrence of a previously experienced Grade 3 event)	Not permitted. Permanently discontinue RXC004	Not permitted. Permanently discontinue RXC004	Not permitted. Permanently discontinue RXC004

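### Table 11 has no liver-specific row for RXC004: restart after a Grade 3 liver event, or continued dosing at Grade 2 level, is possible with liver tests still in the Hy's Law range

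*Protocol*

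**What the plan says.** **Dose rules for RXC004.** Table 11 has specific rows for colitis, dysgeusia, bone events, COVID-19, surgery, vomiting and missed doses. Liver events fall under Other AEs. For a first RXC004-related Grade 3 event the action is "Interrupt RXC004 and provide supportive care, resume a lower dose level when resolved", with resolution defined as Grade 2 or lower, or baseline. A repeat of the same Grade 3 event, or any Grade 4 event, means permanent discontinuation. Table 12 repeats the Grade 2 restart level and gives the reduced dose (1 mg in Module 3). Grading follows one standard: "Toxicity will be assessed using the NCI Common Terminology Criteria for Adverse Event (CTCAE) version 5.0".

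**Holds below Grade 3.** Section 6.5.1 opens permissively ("RXC004 may be dose interrupted (withheld) until a clinically significant (any grade) and/or a grade", continuing with 3 or above). The text after Table 11 is firmer: "RXC004 related toxicities observed during the course of the study will be managed by interruption of RXC004". Neither sentence mentions the liver.

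**Hy's Law.** Section 8.3.6 requires a report within 24 hours and further examinations when AST or ALT is at least 3 x ULN and bilirubin at least 2 x ULN without a known other cause. Section 12.10 adds an event-of-interest report in Module 3 when ALP is below 2 x ULN. Neither states a dose action.

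**Pembrolizumab.** Table 20 (Appendix L) withholds pembrolizumab for a Grade 2 liver event and stops it at Grade 3 or 4. Section 6.5 lets the other agent continue if the investigator sees benefit. Section 6.5.1, in its colitis paragraph, adds: "For patients receiving the combination treatment with RXC004 and pembrolizumab, the most conservative guideline should be followed".

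**Phase 1 experience.** Section 4.4.1.2 reports: "One patient who received 1.5 mg in combination had drug-induced liver injury (DILI), which was considered drug-related and a DLT". Table 5, note c, attributes it as "Related to RXC004 and nivolumab".

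**The concern.** Liver injury is the one dose-limiting toxicity seen at the RXC004 dose chosen for Module 3 when given with an anti-PD-1 antibody. The plan nevertheless handles it by a restart level that is looser than the one for other organ-specific problems. Colitis must settle to Grade 1 or better before RXC004 resumes. After biliary obstruction, Section 8.3.7.1 delays treatment until liver tests are back where they stood before the blockage. After a related Grade 3 liver injury, Grade 2 is enough.

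Two situations follow. A patient recovering from a Grade 3 injury could be re-exposed with liver tests that still signal a possible Hy's Law case. And a patient who reaches the Hy's Law thresholds at Grade 2 level could keep taking RXC004 while the work-up runs, because no text requires a hold at that stage. What is at stake is avoidable exposure during unresolved liver injury, and different handling from site to site.

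**Working it through.** **1. The plan's own figure.** Table 6 gives dose-limiting toxicity at RXC004 1.5 mg plus nivolumab as 1 (13) with N = 8. 1/8 = 12.5%, which rounds to 13%; exact (Clopper-Pearson) 95% CI 0.3 to 52.7%. Among the 6 evaluable patients in Table 5, 1/6 = 16.7%, CI 0.4 to 64.1%.

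**2. Overlap of Grade 2 with Hy's Law, normal baseline.**

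| Test | Grade 2 band (Table 20, note a) | Hy's Law (8.3.6) | Overlap |
|---|---|---|---|
| AST/ALT | above 3 to 5 x ULN | 3 x ULN or more | above 3 to 5 x ULN |
| Bilirubin | above 1.5 to 3 x ULN | 2 x ULN or more | 2 to 3 x ULN |

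A patient in both overlap ranges is Grade 2 on each test. After a Grade 3 event, that patient has reached the stated restart level. Without a preceding Grade 3 event, that patient never reaches the Grade 3 row that makes a hold mandatory.

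**3. Restart ceiling against entry limit (Section 5.1, criterion 5).**
- AST/ALT, no liver metastases: 5/2.5 = 2.0 times the entry limit in Module 3; 5/3 = 1.67 times in Modules 1 and 2.
- AST/ALT, liver metastases: 5/5 = 1.0.
- Bilirubin: 3/1.5 = 2.0; with Gilbert's disease 3/3 = 1.0.
- With an abnormal baseline, note a uses multiples of baseline. From 2 x ULN, the Grade 2 AST/ALT ceiling is 5 x 2 = 10 x ULN.

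**4. Does any other text supply the hold?**
- The opening sentence of 6.5.1 and the any-grade row of Table 11 are discretionary.
- The sentence after Table 11 covers toxicities judged RXC004-related, which the Hy's Law work-up has still to settle. It is not a universal hold either: Table 11 treats Grade 1 colitis by dose reduction without interruption.
- Table 20 acts on pembrolizumab only, and Section 12.8 releases the investigator from it if the event is judged unrelated to pembrolizumab.
- Section 8.3.7.1 concerns obstruction.

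**5. Does Phase 1 show a dose effect?** In Table 8 ("Most common AEs considered related to RXC004 or nivolumab"), related bilirubin increase was 3/8 at 1.5 mg and 0/5 at 1 mg. Of the C(13,3) = 286 ways to place three events, 56 put all three in the group of 8 and 10 put all three in the group of 5. The Fisher two-sided p is (56 + 10)/286 = 0.23. The data are too few to show a dose effect or to exclude one.

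**The case against.** The best defence is that generic rules already reach liver events, and firmly. A related Grade 3 event must be interrupted. Restart is permitted rather than required, and only at a lower dose. Repeat Grade 3 and any Grade 4 events end treatment. In Module 3 the restart dose is 1 mg, at which Phase 1 saw no dose-limiting toxicity in 5 patients on nivolumab. For a Hy's Law case, Section 8 calls for immediate discussion with the sponsor on whether to continue, and once the event is judged related, Section 6.5.1 says it is managed by interruption. For an event that starts at Grade 2, resolution to baseline is the sensible reading. The safety monitoring committee also reviews early combination data.

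Most of this stands, and it limits the point. It does not set a restart level below the Hy's Law range, and it leaves the hold during work-up to judgement. Committee reviews are periodic and do not govern a single patient's dosing. If the most-conservative-guideline sentence were read generally, Table 20 would close much of the gap in Module 3. Its place in the colitis paragraph leaves that open, and Modules 1 and 2 have no pembrolizumab rule to borrow.

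A reader might infer that RXC004 has no rule at all for liver events, or that an investigator cannot hold it at Grade 2. The documents say otherwise on both counts. A reader might also infer that 1.5 mg is more hepatotoxic than 1 mg; one injury attributed to both drugs and the counts in Table 8 do not support that.

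**Conclusion.** The point holds as a gap in a stated rule. RXC004 may restart, at a reduced dose, after a first related Grade 3 liver event with AST/ALT up to 5 x ULN and bilirubin up to 3 x ULN, values that can still satisfy Section 8.3.6. A Hy's Law case at Grade 2 level requires reporting and work-up but no RXC004 hold.

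The limits quoted assume a normal baseline. For patients with liver metastases or Gilbert's disease who enter at the upper limits, the same ceilings equal the entry limits, so a fixed multiple of ULN would not suit them. The clinical evidence is one patient, on nivolumab rather than pembrolizumab; Section 12.3.1 itself expects the two combinations to have similar safety. This is a worthwhile, inexpensive improvement. It is not evidence that the dose is unsafe.

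**What to change.** Add a liver row to Table 11 and align Table 12:

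1. After an RXC004-related Grade 3 liver event, restart at the reduced dose only at Grade 1 or lower, or baseline.
2. When the Section 8.3.6 criteria are met, hold RXC004 until the work-up is complete. Discontinue if no other cause is found. Once obstruction is shown, follow Section 8.3.7.1.
3. For patients who enter at or above either limit (AST/ALT up to 5 x ULN with liver metastases, bilirubin up to 3 x ULN with Gilbert's disease), set the trigger as a multiple of baseline, as Table 20 note a already does for grading. The sponsor should choose the multiple.
4. State in Section 6.5.1 that the most-conservative-guideline sentence also covers liver events in Module 3.

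The cost is one table row and a few sentences in an amendment; the liver tests are already collected (Table 13). Some patients will have extra RXC004 holds and lose dose intensity, including obstruction cases held until the cause is known. How often cannot be bounded from the documents: the trigger needs both tests raised, their overlap is not reported, and the Phase 1 counts of related events do not include obstruction.
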